Harnessing the Power of Technology: MOMBA for Postpartum Smoking NCT02237898

09/07/2017

Overview: Through a pilot, randomized control trial tested the effectiveness of Momba Live Long (the Momba Live Long application and sensor) on 7-day point prevalence of smoking abstinence rates i) at the end of the trial and ii) at 3-month follow-up as determined by the Timeline Follow Back instrument and number of negative breath tests.

The randomized controlled trial of Momba Live Long utilized a control group which received financial incentives at an in-person office/clinic visit based on expired CO levels obtained through the piCO+TM CO sensor compared to the MoMba Livelong application. We used results from frequently administered assessment instruments over the course of an 3-month period and subsequent 6- and 12-month follow ups to assess outcomes and to examine the reliability and validity of assessment measures, and key methodological parameters, such as effect size, proportion of eligible and willing study participants, attrition rate, time necessary for data collection, and necessary skill sets for CMHAs. The RCT involved an intervention arm (10 women who receive Momba Live Long) and "control" arm (10 women who receive financial incentives delivered in-person in the office). Participants were randomized using a number generation mechanism provided to the CMHAs who are screening and enrolling women.

Intervention Group (Momba Live Long): The intervention group received a smartphone, data plan, Momba Live Long, including the Bluetooth enabled CO sensor, and training from a CMHA on its use. The intervention group did most of its CO tests remotely, outside of a baseline, 3-month end point assessment, and 6-month and 12-month follow-ups. However, participants also came n for the first 5 days of week 1 to be trained on how to use the Sensordrone and Momba Live Long app. As part of this training, we showed the intervention group participants a Demonstration Video and a Powerpoint Presentation about how to use the Momba Live Long Application. Intervention group participants came to the office for a visit in Week 4 and Week 8 to calibrate the Sensordrone and to submit a urine specimen.

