For the RCT dependent variables are the 7-day point prevalence of smoking abstinence rates i) at the end of the trial and ii) at 3-month follow-up. We will also compare 2-week continuous smoking abstinence rates at these time points. Smokers are considered abstinent based on self-reported smoking abstinence verified by CO levels <6 ppm and self-report abstinence based on the Timeline Follow Back. (50) Because abstinence is categorical, a binary random effects logit model will be used. (51) As a secondary analysis, we will add an indicator variable for intensity of utilization for Momba Live Long application to the model in order to determine if it contributes significantly to response. Given that this is a pilot, we are not powered

to detect a significant difference on our outcomes. However, we will develop effect sizes to estimate power for a larger study and we will evaluate the direction and consistency of effects. We use guidelines for Stage 1b studies, which suggest 15-30 participants per cell. (52) For the outcome of 7-day point prevalence for smoking abstinence at the end of the trial, and 15 subjects per condition, a 2-tailed alpha of .05 we will have power of 90% if we have the same effect size found in other studies of contingency management with perinatal women smokers. (34) In all likelihood, the effect will be smaller for the 3-month outcomes. However, these results will provide a reasonable estimate with which to power a larger study.

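### The plan calls the pilot's effect a reasonable estimate for powering a larger study, but with 10 or 15 women per arm the observed difference is too imprecise to serve as a planning value

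*Combined protocol and SAP*

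**What the plan says.** The Overview sets the pilot's size: "an intervention arm (10 women who receive Momba Live Long", with a control "arm (10 women who receive financial incentives delivered in-person in the office". It also lists effect size among several methodological parameters to be examined.

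The Data Analysis for Pilot RCT section admits that the trial is not powered to detect a difference, and continues: "However, we will develop effect sizes to estimate power for a larger study". It then gives a power statement for a different number of women, "15 subjects per condition, a 2-tailed alpha of .05 we will have power of 90" percent, with the effect borrowed from other contingency management studies. It expects a smaller effect at 3 months and closes: "However, these results will provide a reasonable estimate with which to power a larger study".

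No confidence interval for the pilot effect, minimum important difference or other allowance for imprecision is mentioned.

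**The concern.** The natural reading is that the between-arm effect seen in this pilot will be the input to the next study's sample-size calculation. Required sample size varies roughly with the inverse square of the difference, so error in a small pilot's estimate is greatly magnified in the planned size. A chance null could end work on a useful application. A chance large difference could lead to a study that enrols women but cannot answer its question. The sentence tells the reader that the estimate is fit for this use, so the matter is a claim about the design and not only how a later team might behave.

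**Working it through.** **The plan's own figure.** The 90% power cannot be reproduced, because no abstinence rates or effect size are given. Solving backwards with the pooled two-proportion formula, 15 per arm at two-sided 0.05 needs a difference of about 48 to 56 points (for example 20% v 75%). For the same rates, 10 per arm gives 73%.

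**Inputs.** From the documents: 10 per arm (Overview), 15 per arm and two-sided alpha 0.05 (Data Analysis for Pilot RCT), and a binary outcome, 7-day point prevalence abstinence. Assumed: the true abstinence rates, varied below, and 80% power for the larger study. Dropout is ignored; it would widen the error.

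**Step 1: the correct size.** Per arm,

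n = [1.96·√(2p̄(1−p̄)) + 0.8416·√(p₁(1−p₁) + p₂(1−p₂))]² / (p₁−p₂)².

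For 50% v 30%, p̄ = 0.40, so n = [1.96·√0.48 + 0.8416·√0.46]² / 0.04 = (1.358 + 0.571)² / 0.04 = 93.

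**Step 2: precision of the pilot difference.** At those rates the 95% half-width is 1.96·√(0.46/10) = 42 points with 10 per arm and 1.96·√(0.46/15) = 34 points with 15. For an observed 5/10 v 3/10, the Wilson limits are 0.237 to 0.763 and 0.108 to 0.603. The Newcombe interval is therefore

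- lower: 0.20 − √(0.263² + 0.303²) = −0.20
- upper: 0.20 + √(0.263² + 0.192²) = +0.53

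that is, about −20 to +53 points.

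**Step 3: what one woman does to the planned size.** Against 3/10 in the office arm, the Step 1 formula gives 356 per arm if 4/10 abstain with the application, 93 if 5/10, 42 if 6/10 and 24 if 7/10.

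**Step 4: all possible pilots.** Every pair of counts was given its exact binomial probability. Pairs with the application arm ahead were converted to a planned n by Step 1, and the true power at that n was computed at the true rates. A pilot fails if the difference is zero or reversed, or if the planned n gives less than 80% true power.

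| True rates | Pilot per arm | Correct n per arm | Zero or reversed | Fails |
|---|---|---|---|---|
| 50% v 30% | 10 | 93 | 24% | 72% |
| 50% v 30% | 15 | 93 | 17% | 68% |
| 40% v 20% | 10 | 82 | 22% | 70% |
| 60% v 30% | 10 | 42 | 12% | 61% |
| 60% v 20% | 10 | 23 | 4% | 53% |
| 75% v 20% | 10 | 12 | under 1% | 53% |

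For the first row, 63% of the pilots with a positive difference plan too few women, so 24% + 76% × 63% = 72%. Among those positive pilots the median planned size is 42 per arm (interquartile range 23 to 97). At 42 per arm the true power is Φ[(√42 × 0.20 − 1.358)/0.678] = 46%. Over all pilots at these rates, 42% give less than half the correct size, 16% more than twice it, and 18% fall within a factor of 2.

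**Reading the failure rate.** An estimate that errs equally often in either direction would plan too few women about half the time, however large the pilot. The 53% figures are therefore close to that benchmark. The evidence lies in the excess at 20- and 30-point differences and in the spread of planned sizes.

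**The case against.** **The plan already disclaims power.** It does, and that counts in its favour, but the disclaimer concerns significance testing. The later sentence says the estimate is nonetheless good enough for planning, and the same small sample defeats that too.

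**The assumed rates drive the result.** This stands in part. If mis-sized means wrong by more than a factor of 2, the claim holds for true differences of 10 to 30 points (55% to 84% of pilots), but at 60% v 20% the size is within a factor of 2 in 53%. Near the effect implied by the 90% power statement, only 28% to 34% are mis-sized. So large an effect is a doubtful guide here, because the Control Group section says both arms receive contingency management and only its delivery is compared.

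**The use is inferred.** The plan does not say that an unadjusted point estimate will go into a formula, and it does not rule out intervals. That is fair; the failure rates above are conditional on the observed difference being used.

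**Stronger readings a reader might infer.**

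- That the pilot will usually lead to no further trial or to one far too small. Taking far too small as true power below 50%, the combined share is about 66% for 50% v 30% and 62% for 40% v 20% with 10 per arm. It is only 47% for 50% v 30% with 15 per arm and 40% for 60% v 30% with 10, so this does not hold generally.
- That the odds ratio from the planned model ("Because abstinence is categorical, a binary random effects logit model will be used") will be mistaken for a ratio between two marginal rates, shrinking the next study further. Nothing in the documents says it will be used that way, and they give no between-woman variance from which to size the effect. The dependent variables are abstinence rates, from which a risk difference is directly available.
- That the pilot fails at its main purpose. The Proposed Analytic Plan makes feasibility and acceptability the goal, and the section on standardized measures labels smoking prevalence secondary. Those aims are unaffected.

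**The remedy is imprecise too.** True: an in-office rate of 3/10 has a Wilson interval of about 11% to 60%. But if a 20-point difference is fixed for illustration, Step 1 gives 64 per arm at 11% v 31%, 97 at its peak (40% v 60%) and 82 at 60% v 80%. That is a far narrower range than the 24 to 356 in Step 3.

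**Conclusion.** Wrong as written: the plan states a property that the design does not have. At an assumed 50% v 30%, a study sized on the observed difference would miss 80% true power in 72% of cases with 10 per arm and 68% with 15, so settling which number applies would not cure it. With 10 per arm and the other assumed rates of 40% v 20%, 60% v 30% and 60% v 20%, the figures are 70%, 61% and 53%. These rest on true rates the documents do not supply, on an 80% power target, on no dropout, and on direct use of the observed difference. The imprecision itself, an interval of about −20 to +53 points for 5/10 v 3/10, needs no assumed truth. The point should be fixed, but it is not critical: no assignment, endpoint, test or conclusion of this pilot changes.

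**What to change.** Replace the two sentences on powering a larger study with text to this effect:

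- The between-arm difference in abstinence will be reported as a risk difference with its 95% CI, and is not itself a planning value.
- The larger study will be sized on a minimum important difference, or a non-inferiority margin, justified in its own protocol.
- The pilot will inform that calculation through participation, retention, compliance and the in-office abstinence rate, each with a 95% CI. A short table will show the required size across those intervals, because these quantities are imprecise too.

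Separately, reconcile the 10 per arm in the Overview with the 15 in the power statement.

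The cost is a wording change and one table, with no new data collection. The pilot's stated yield becomes less favourable. Participation and retention are already planned, with thresholds of 60% and 80%, so most of the replacement is work the plan already contains.
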